**8. How good are the facilities provided to manage SCD patients?**

A. Very good [ ]  
B. Good [ ]  
C. Neither good nor poor [ ]  
D. Poor [ ]  
E. Very poor [ ]

---

**9. If the facilities have any problems, please state them below**

---

**10. How satisfied are you with the management of your clinic?**

- A. Very satisfied [ ]
- B. Satisfied [ ]
- C. Neither satisfied nor dissatisfied [ ]
- D. Dissatisfied [ ]
- E. Very Dissatisfied [ ]

**11. Do you feel protected from injuries and professional risks?**

- A. Very good [ ]
- B. Good [ ]
- C. Neither good nor poor [ ]
- D. Poor [ ]
- E. Very poor [ ]

**12. How do you judge your involvement in the decision-making process of your centre?**

- A. Very good [ ]
- B. Good [ ]
- C. Neither good nor poor [ ]
- D. Poor [ ]
- E. Very poor [ ]

**13. How satisfied are you with your career advancement (if you are willing to)?**

- A. Very satisfied [ ]
- B. Satisfied [ ]
- C. Neither satisfied nor dissatisfied [ ]
- D. Dissatisfied [ ]
- E. Very Dissatisfied [ ]

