### 3.2. Sample size determination

As pilot experience, the questionnaires will be administered to 30 SCD patients or parents/legally designated representatives of children affected by SCD and 30 Professionals working with SCD patients (mainly doctors and nurses) in each centre for a total of 120 patients and 120 health workers. A focus group discussion will be run with the SCD patients/parents. Following the pilot study, a wider survey will be launched involve patients, parents and healthcare professionals in the whole country and in other centres involved in the project.

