### 3.3. Setting

The study will be conducted in the following four centres: Barau Dikko Teaching Hospital Kaduna State University (BDTH), Ahmadu Bello University Teaching Hospital Zaria (ABUTH), National Hospital Abuja (NHA), and Federal Medical Centre Katsina (FMC).

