## 4. Inclusion and exclusion criteria

The following inclusion criteria will apply for patients/parents:

- Aged  $\geq 18$
- Have SCD diagnosis or having a child with a SCD diagnosis
- Attending the centre from at least 6 months
- Nigerian nationality
- Informed Consent signed

The following inclusion criteria will apply for healthcare professionals:

- Working in a SCD clinic
- At least 5 years of experience with SCD patients
- Informed Consent signed

The following exclusion criteria will apply for all participants:

- Informed consent form withdrawal
- Illiterate subjects
- Any psychiatric conditions impairing the participation in this study.

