## 5. Study procedure

### 5.1. Questionnaire completion

After obtaining the informed consent, subjects (patients, parents/legally designated representatives and healthcare professionals) will be asked to complete the questionnaire. Two questionnaires have been developed, one addressed to patients, parents, legally designated representatives (Annex I) and another one for healthcare professionals (Annex II)

The following measures will be adopted to reduce the interviewer effect:

- The investigator will give instructions to complete, but questionnaires will be self-completed.
- Participants will have time to complete the questionnaire in a private setting.
- Completed questionnaires will be blindly deposited in a closed box. This will be thus safeguarded by the investigators.
- Completed questionnaires will be returned to the coordinating investigator for analysis.

Questionnaires will be pseudonymised: an alphanumeric code will be indicated on each questionnaire and reported on the corresponding informed consent form.

All the study investigators are researchers/officers in the centres not involved in patients' clinical management. The veracity and consistency of responses are of paramount importance for the

---

validity of the study and the improvement of the management of SCD patients: all the actions necessary to allow the participants to freely express themselves will be adopted.

Together with the questionnaire, participants will receive information about the time and venue for the focus group discussion (Annex III). For those who are willing, reminders about the focus group will be sent by e-mail/phone.

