### **5.4. Data analysis**

Data will be managed by the study investigator, his delegates and authorised people (e.g. the hosting institution staff, statisticians, IT people). Data will be analysed by the coordinating investigator. SPSS and Thematic Analysis will be performed.

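### Annex II item 13 is worded as conditional but has no box for staff outside the condition, so the base for its satisfaction share cannot be known

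*Protocol*

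**What the plan says.** In Annex II, Section B, item 13 reads "How satisfied are you with your career advancement (if you are willing to", where the bracket closes the question. Five boxes follow, running from very satisfied to very dissatisfied, with "C. Neither satisfied nor dissatisfied" as the midpoint. The item has no not-applicable box, filter question or skip instruction. Other items in the same annex do offer a way out: item 1 has a none-of-the-above option, and several items have a free-text other option.

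Section 5.1 fixes how the form is filled in: "The investigator will give instructions to complete, but questionnaires will be self-completed". Participants complete it in private and drop it in a closed box.

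Section 3.2 plans for "30 Professionals working with SCD patients (mainly doctors and nurses) in each centre", "for a total of 120 patients and 120 health workers". Section 5.4 says of the analysis only that "SPSS and Thematic Analysis will be performed". A denominator or a rule for blanks may be set in an analysis plan that is not at hand, and its absence here is not the point.

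**The concern.** The stem sets a condition and the answer boxes ignore it. A health worker who does not want advancement has two choices: tick a rating, or leave the item empty. A tick in the middle box is indistinguishable from real neutrality. A blank is indistinguishable from an overlooked or refused item. Because the form goes into a closed box without an interviewer, nobody sorts this out at the time.

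The bracket is also ambiguous. It may mean willing to advance, or willing to answer. Under the second reading the item is simply optional, and a blank carries yet another meaning.

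The primary objective in Section 3.1 covers the needs of health workers as well as patients. Item 13 is the only closed career question put to all staff: the option on poor career prospects after item 17 is offered only to those who say they are not satisfied with their work overall. A worker who is content overall but has an unmet career need is therefore caught by a closed question only here. Section 3.2 also announces a wider survey after the pilot, and a flaw in the form may carry into it.

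**Working it through.** **Stated figure.** Section 3.2 gives 30 health workers per centre and Section 3.3 lists four centres: 30 × 4 = 120, which agrees with the stated total.

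**Inputs not in the protocol (assumptions).** Let *q* be the share of staff not seeking advancement, taken as 10% to 40%, and *p* the share dissatisfied among those who are, taken as 50% (30% as a second case). N = 120.

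**Case 1: staff not seeking tick the middle box** (or leave a blank but stay in the denominator). Recorded share = p(1 − q).

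| q | Not seeking | Seeking | Dissatisfied (p = 50%) | Recorded share of 120 | Share of seekers |
|---|---|---|---|---|---|
| 10% | 12 | 108 | 54 | 45% | 50% |
| 20% | 24 | 96 | 48 | 40% | 50% |
| 30% | 36 | 84 | 42 | 35% | 50% |
| 40% | 48 | 72 | 36 | 30% | 50% |

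With p = 30% the recorded share is 27%, 24%, 21% and 18%.

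**Case 2: all of them leave a blank, and only respondents are counted.** Recorded share = p(1 − q)/(1 − q) = p. There is no shift. But 12 to 48 forms (0.1 × 120 to 0.4 × 120) would look like item non-response.

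**Case 3: half tick the middle box and half leave a blank, respondents only.** Recorded share = p(1 − q)/(1 − q/2). With p = 50%: 54/114 = 47.4% at q = 10%, and 36/96 = 37.5% at q = 40%.

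**Why the form cannot settle which case holds.** Take 48 dissatisfied out of 120 completed items. If everyone seeks advancement, the share among seekers is 48/120 = 40%. If 24 of those in the middle box are not seeking, it is 48/96 = 50%. The completed forms are identical in both situations. In one centre of 30 the same contrast is 12/30 = 40% against 12/24 = 50%.

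**Scale.** At q = 20% and p = 50%, the 95% half-width for the share among seekers is 1.96 × √(0.5 × 0.5/96) = 10 points overall and 1.96 × √(0.5 × 0.5/24) = 20 points in one centre. The assumed 10-point shift is thus about as large as the sampling error for all staff and half of it within a centre. Unlike sampling error, it would not shrink in a larger survey.

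**The case against.** The strongest reply is that nothing is distorted. Staff who do not want advancement have no unmet advancement need, so the dissatisfied count over all 120 is a correct share of all staff, and the protocol does not name the share among seekers as its target. This stands as far as it goes: the 45% to 30% range is an understatement only if the figure is read as applying to staff who seek advancement. But that is the group the stem points to, if the bracket means willing to advance, and the form cannot identify it.

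A reader might infer that blanks also bias the result. They do not when only respondents are counted (Case 2); they only make the base uncertain.

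A reader might also infer that the affected group is large because Section 4 requires "At least 5 years of experience with SCD patients". The protocol says nothing about grade, career stage or wish for promotion, so that inference has no support. Nor does it support the idea that such staff would mostly choose the middle box. Some may truthfully tick satisfied, which is a real answer to the question as a rating by all staff.

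If the bracket means willing to answer, no subgroup is excluded and a blank is voluntary non-response. That reading is possible, but a respondent cannot know which one is meant, so the ambiguity is a reason to reword the item.

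Finally, career advancement is not named in the objective, which refers particularly to disease management in the centre, and item 18 lets all staff raise career needs in their own words. Both are true, and they limit the importance of the point.

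An analysis plan could choose a denominator, but it could not recover a distinction that the printed form never recorded.

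**Conclusion.** The point holds in a limited form. Item 13 has a conditional or ambiguous stem and no box for staff outside the condition, so its base is unknown and cannot be reconstructed after collection. If staff not seeking advancement tick the middle box, the share dissatisfied among seekers is understated: 45% down to 30% instead of 50%, on the assumptions that half of seekers are dissatisfied and 10% to 40% of 120 staff are not seeking. Both inputs are illustrative, so the actual size is unknown and could be negligible.

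The documents do not support saying that the share of all staff is wrong, or that blanks shift a respondents-only share. The severity is minor: one item of 18 in Section B of a descriptive pilot, with an open question as a partial backstop.

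**What to change.** Remove the bracketed condition from the stem of item 13 and add a sixth box: *Not applicable – I am not seeking advancement*. Report the number who tick it, the number blank, and satisfaction among the remaining respondents. In the example with q = 20% and p = 50%, this returns 48/96 = 50% with 24 shown as not applicable, and a share of all staff can still be given from the same counts.

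The cost is one box and a shorter stem before printing, with no added burden for respondents. If forms are already in use, make the change for the wider survey. In the pilot, report all five boxes and the blanks as counts, and do not present the result as a share among staff seeking advancement.

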**14. How satisfied are you with the level of responsibility you have?**

- A. Very satisfied [ ]
- B. Satisfied [ ]
- C. Neither satisfied nor dissatisfied [ ]
- D. Dissatisfied [ ]
- E. Very Dissatisfied [ ]

**15. How satisfied are you with on the decision-making autonomy you have?**

---

---

A. Very satisfied [ ]  
B. Satisfied [ ]  
C. Very Dissatisfied [ ]  
D. Dissatisfied [ ]  
E. Neither satisfied nor dissatisfied [ ]

**16. How do you judge the level of appreciation of your work?**

A. Very good [ ]  
B. Good [ ]  
C. Neither good nor poor [ ]  
D. Poor [ ]  
E. Very poor [ ]

**17. In general, are you satisfied with your work with SCD patients?**

A. Yes  
B. No

**If not, please indicate the reason:**

A. Poor collaboration from colleagues and other staff [ ]  
B. Poor collaboration from patients [ ]  
C. Work overload [ ]  
D. Poor training [ ]  
E. Poor equipments [ ]  
F. Poor organisation [ ]  
G. Poor career possibility [ ]  
H. No social/psychological support [ ]  
I. Inadequate economic renumeration [ ]  
J. Other (please specify) \_\_\_\_\_

**18. In general, what do you think is more important to improve your work?**

---

---

---

### Annex III. FOCUS GROUP INTERVIEW GUIDE

**Topic: Needs Assessment of patients and health workers involved in SCD management.**

**Introduction:**

Hello and welcome to our session. My name is [name], a researcher from **“African Research and Innovative initiative for Sickle cell Education: Improving Research Capacity for Service Improvement” (ARISE)** project, assisting me is .....

Thank you for taking your time to join us to talk about the needs assessment of patients involved in SCD management.

The aim of this discussion is to understand the needs of patients involved in SCD management. We will be discussing on your perceptions and understanding. The discussion will last from 45 minutes to one hour.

As part of the focus group, facilitators will ask questions related to your own perception on health workers and the facilities involved in SCD management. In order to have a fruitful discussion, participants are encouraged to speak one person at a time. Please you are to keep in mind that there are no “negative or positive” comments to any question that will be asked. The purpose is to stimulate conversation and hear the opinion of everyone in this room. I hope you will be comfortable speaking honestly and sharing your ideas with us.

Please note that this session will be recorded, and notes will be taken during the focus group to ensure that we don't miss any of your comments due to their importance. Unfortunately, we can't write fast enough to get them all down that is why we must record them. However, the comment from the focus group will remain confidential and your name will not be attached to any comment. Do you have any question before we begin? Thank you.

1. Please share with me your perception of the health workers in this clinic.
2. Please share with me your perception of the services provided in this clinic.
3. Please share with me your perception of the facilities both in the clinic and lab (e.g. adequacy and functioning).
4. What do you perceive as major need concerning the management of your disease in the clinic?
5. What is the most satisfactory aspect of the management of your disease in the clinic?
6. Is there anything we haven't discussed that you think is important regarding the needs of patients involved in SCD management?
